9.1.1.1 Early Stopping

In the case of stopping the study early due to low recruitment, no inferential efficacy analysis will be carried out. Figures will not be presented. Only summaries and listings of the study population, primary and secondary efficacy endpoints, and safety data will be produced.

The list of outputs produced in case of early stopping of the study is provided in Appendix 1: List of Tables, Figures and Listings.

9.1.1.2 Blinded Model Fitting

Prior to database lock the models to be used in the primary analysis will be examined on the blinded data in order to determine which baseline factors may have a prognostic effect and should be included in the models. The covariates defined in [Section 7.2](#) will be examined in a model of trough S/F ratio and selected as covariates for the relevant model at a 5% level of significance using forward stepwise selection.

Baseline S/F ratio will be the first fitted term in the model regardless of significance. A maximum of 3 further covariates may be included in the model in order to avoid over-parameterization and a reduction in the efficiency of the treatment estimates.

Distributional assumptions underlying the models used for analysis will be also be examined during the blinded review by obtaining a normal probability plot of the residuals and a plot of the residuals versus the

fitted values (i.e. checking the normality assumption and constant variance assumption of the model respectively) to gain confidence that the model assumptions are reasonable.

If the distributional assumptions underlying the model are found not to be reasonable, a log-transformation of the response variable will first be considered. In this event, the LS mean treatment ratio will be presented instead of the LS mean treatment difference. If this model is also found to violate the distributional assumptions, then further models including other transformations or nonparametric alternatives will be explored. An addendum to the SAP will be produced prior to database lock and unblinding detailing the methods to be used will be produced detailing the model strategy to be used in this event.

This approach to the inclusion of baseline covariates which may have a prognostic effect on response will also be used for the Cox proportional hazards and Fine and Gray models to be used for the secondary analyses.

9.2 Primary Efficacy Analysis

9.2.1 Primary Efficacy Estimand

The primary estimand will be the effect of EDP1815 compared to placebo on the change from baseline to trough S/F ratio in Days 1-14.

The population summary measure of interest will be the difference in mean change from baseline in trough S/F between EDP1815 and placebo.

Intercurrent events will be accounted for in the following manner:

Table 9 Intercurrent Event Strategies for the Primary Estimand

Intercurrent event	Strategy to account for intercurrent event
Treatment discontinuation before the end of the 14-day treatment period	Treatment policy Trough S/F ratio will be taken as the lowest recorded value on or off treatment
Death prior to day 14	Composite Trough S/F ratio will be imputed as 0
Discharge prior to day 14	While-on-treatment Trough S/F ratio prior to discharge will be used. Participants will be assumed to remain above trough value after discharge.
Withdrawal from the study prior to day 14.	While-on-treatment Trough S/F ratio prior to starting study withdrawal will be used

9.2.2 Main Analytical Approach

Trough S/F ratio and change from baseline in trough S/F ratio will be summarized and listed.

Change from baseline in trough S/F ratio will be analyzed with an analysis of covariance (ANCOVA) model. The model will include fixed effect parameters for treatment and baseline S/F ratio together with the additional baseline covariates which were identified during the blinded review.

Least square (LS) estimates of the mean change from baseline trough S/F ratio together with the standard error and 95% confidence interval will be reported. The LS mean treatment difference and 95% confidence interval will also be presented.

The distributional assumptions for the final unblinded model will be checked in the same manner as described above in [Section 9.1.1.2](#). If the inclusion of treatment effect causes the models to no longer be valid compared to the blinded data models, a Wilcoxon test will be used to compare the treatments instead and only a p-value will be produced for the comparison.

9.2.3 Sensitivity Analyses

A sensitivity analysis will be performed where no imputation of trough S/F ratio will be made for participants who die. Instead the lowest reading recorded prior to death will be used.

If a newly approved medication for COVID-19 becomes part of the standard of care treatment at the investigational site during the study an additional sensitivity analysis will be performed. A new medication covariate (yes, no for use before Day 14) will be fitted into the ANOCOVA model used for the main analytical approach together with its interaction with the EDP1815 treatment term.

In addition to the estimates of LS means for effect of each treatment group and their difference, the p-values for the significance of the new medication*treatment interaction will be provided.

9.2.4 Subgroup Analyses

If the sensitivity analysis for a newly approved COVID-19 medication described in [Section 9.2.3](#) is performed and the p-value for the new medication*treatment interaction is found to be significant at the 5% level, the analysis described for the main analytical approach will be performed by use of the new medication prior to Day 14.

9.3 Secondary Efficacy Analyses

9.3.1 Change from Baseline in S/F Ratio

9.3.1.1 Estimands

The endpoints will be the change from baseline in S/F ratio as measured on Days 4, 7, 10 and 14. The population summary measure of interest will be the difference in mean change from baseline in S/F ratio between EDP1815 and placebo at the relevant study day.

The intercurrent event strategy for these estimands is described in [Table 10](#).

Table 10 Intercurrent Event Strategies for the Change from Baseline in S/F Ratio Secondary Estimands

Intercurrent event	Strategy to account for intercurrent event
Death prior to the study day of interest	Composite S/F ratio will be imputed as 0
Discharge prior to the study day of interest	Composite Last S/F ratio prior to discharge will be used. Participants will be assumed to remain above this value after discharge.
Treatment discontinuation before the study day of interest without withdrawal from the study	Treatment policy The actual S/F ratio reported at the timepoint will be used regardless of treatment discontinuation
Withdrawal from the study prior to the study day of interest.	While-on-treatment Participants will be excluded from the analysis at that study day

Data missing for reasons other than an intercurrent event will be imputed as defined in [Table 5](#).

9.3.1.2 Analytical Approach

Actual values and change from baseline in S/F ratio will be summarized at Days 4, 7, 10, and 14 and all daily S/F ratio data will be listed. This summary will be produced once showing only available data with no imputation and once after the rules specified in [Table 5](#) have been applied.

Mean (+/- standard error (SE)) S/F ratio and change from baseline in S/F ratio will be plotted by study day for Days 1-14, once using only available data with no imputation and once after the rules specified in [Table 5](#) have been applied.

As missing data due to the intercurrent events of death, discharge and initiation of another experimental treatment cannot be considered missing at random, a mixed model for repeated measures is not considered an appropriate analysis for this data. As such, the endpoint at each study day will be analyzed using separately using ANCOVA models.

Two models will be fitted at each study day, one with S/F ratio as the response variable and one with change from baseline in S/F ratio as the response variable. The models will include treatment and baseline S/F ratio together with the additional baseline covariates included in the primary analysis model for trough S/F ratio.

LS mean and LS mean change from baseline in S/F ratio will be reported with their corresponding standard error and 95% confidence interval. Estimated treatment difference for the mean change from baseline and corresponding 95% confidence interval will also be reported.

LS mean (95% CI) change from baseline in S/F ratio will be plotted against time for Days 4, 7, 10 and 14.

The distributional assumptions for the final unblinded model will be checked in the same manner as described above in [Section 9.1.1.2](#).

A sensitivity analysis will be performed where no imputation will be used for participants who die. These participants will be excluded from the analysis at any timepoints after death has occurred.

If at least 10% of participants have withdrawn from the study before Day 14, a sensitivity analysis will be performed. Data for participants who have either been discharged or died will be imputed as per the rules in [Table 5](#), but no other imputation will be performed. The change from baseline in S/F ratio will be analyzed in a mixed model for repeated measurements including treatment, baseline S/F ratio, study day, study day*treatment and study day*baseline S/F ratio and any additional covariates identified during the blinded modelling phase. Data from all study days between Day 1 and Day 14 would be included.

LS mean change from baseline in S/F ratio will be reported with their corresponding standard error and 95% confidence interval at Days 4, 7, 10 and 14. Estimated treatment difference for the mean change from baseline and corresponding 95% confidence interval will also be reported at these study days.

If a newly approved medication for COVID-19 becomes part of the standard of care treatment at the investigational site during the course of the study an additional sensitivity analysis will be performed at each visit in the same manner as described in [Section 9.2.3](#). A new medication covariate (yes, no for use before the relevant study day) will be fitted into the ANOCOVA models at each visit together with its interaction with the EDP1815 treatment term.

In addition to the estimates of LS means for effect of each treatment group and their difference, the p-values for the significance of the new medication*treatment interaction will be provided at each visit. Mean (+/- standard deviation) S/F ratio at each study day will also be plotted once using only available data and once after the rules specified in [Table 5](#) have been applied.

9.3.2 Percentage Change from Baseline in S/F Ratio

Percentage change from baseline in S/F ratio at Days 4, 7, 10 and 14 will be summarized and analyzed in the same manner as described for mean change from baseline in S/F ratio in [Section 9.3.1](#).

9.3.3 WHO OSCI Score

9.3.3.1 Estimands

The endpoints will be recorded (inpatients) or derived (outpatients) WHO OSCI score at Days 4, 7, 14, 21 and 42. Population summary methods will be:

- Percentage of participants at each level of the WHO OSCI score
- Percentage of participants with each possible shift from Baseline in WHO OSCI score
- Percentage of participants remaining at their baseline WHO OSCI score (or lower)

- Percentage of participants reporting each level of WHO OSCi score at their worst post-baseline day

The intercurrent event strategy for these estimands is described in [Table 11](#).

Table 11 Intercurrent Event Strategies for the WHO OSCi Score Secondary Estimands

Intercurrent event	Strategy to account for intercurrent event
Death prior to the study day of interest	Composite WHO OSCi score of 8 will be carried forward to all further study days
Discharge prior to the study day of interest	Treatment policy The WHO OSCi score will be derived from the participant daily diary using the rules in Section 5.3.3.4
Treatment discontinuation before the study day of interest and no other experimental treatment not considered standard of care initiated	Treatment policy WHO OSCi score used as recorded for inpatients or derived for outpatients from the participant daily diary using the rules in Section 5.3.3.4
Withdrawal from the study due to initiating other experimental treatment not considered standard of care before the study day of interest	While-on-treatment Participants will be excluded from the analysis at that study day

Data missing for reasons other than an intercurrent event as detailed above will not be imputed.

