7.1 Discontinuation from Study Treatment and/or Withdrawal from the Study

Participants may discontinue from study treatment or withdraw from the study at any time and for any reason without prejudice to their future medical care by the investigator or at the study site. Every effort should be made to keep participants in the study. The reasons for participants discontinuing treatment and/or withdrawing from the study will be recorded in the CRF. A participant may discontinue from the study drug or withdraw for the following reasons:

1. The participant does not meet the protocol inclusion or exclusion criteria.
2. The participant is non-compliant with the protocol.
3. The participant is admitted to ICU. At this point, dosing for this individual subject will be stopped, but they will remain in the study until Day 42 for data collection where practical. However, if the subject is eligible for another interventional trial, they may be enrolled into this trial after discussion with the chief investigators. The participant is deemed to have completed this study at the point of signing the informed consent of this other study.
4. The participant has a serious or intolerable AE that in the investigator's opinion requires discontinuation from study treatment or withdrawal from the study (see section 7.2).
5. The participant has laboratory safety results that reveal clinically significant changes from the baseline values that are not, in the opinion of the investigator, explained by COVID-19 infection or CRCs.
6. The participant is lost to follow-up.
7. Other reasons (e.g. pregnancy).
8. The participant withdraws consent, or the investigator or sponsor decides to discontinue the participant's participation in the study.

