9.3.2. Secondary Efficacy Estimands

All secondary endpoints defined in Section 3 will be considered on the ITT population.

Intercurrent events strategies will be dependent on whether the endpoint is one evaluating the Objective 1 (to evaluate the effect of EDP1815 on the development and severity of complications of COVID-19 infection) or Objective 2 (To evaluate the effect of EDP1815 on length of hospitalization and recovery in participants with COVID-19) as follows:

Table 7: Intercurrent Event Strategies for the Secondary Estimands

Intercurrent event	Strategy for endpoints relating to Objective 1	Strategy for endpoints relating to Objective 2
Treatment discontinuation before the end of the 11 day treatment period	Treatment policy Actual values will be used regardless of treatment discontinuation	
Death prior to time of endpoint evaluation	Composite Subjects who die will be given a worst-case value from time of death	Competing risk Deaths will be accounted as a competing risk
Discharge prior to time of endpoint evaluation	While on treatment ¹ Values up to the time of discharge will be used. Treatment policy ² Actual values will be used regardless of inpatient/outpatient status	Treatment policy Actual values will be used regardless of inpatient/outpatient status
Initiating other experimental treatment not considered standard of care before endpoint evaluation	While-on-treatment Values prior to starting experimental treatment will be used	

¹ This will be used for all endpoints which are not recorded after discharge (e.g. S/F ratio).

² This will be used for all endpoints which are recorded after discharge (e.g. those relating to the WHO OSCI scale).

Population level summary measure will be assigned as appropriate to the type of endpoint as follows:

Table 8: Population Level Summary Measures for the Secondary Estimands

Type of endpoint	Population level summary measures
Categorical endpoint	Summary statistics, p-value for treatment difference (CMH test)
Binary endpoint	Risk difference between EDP1815 and placebo
Continuous endpoint	Mean difference between EDP1815 and placebo
Number of days with an event	Summary statistics
Time to event	Hazard ratio for EDP1815 vs. placebo

Full details of the individual secondary efficacy estimands will be provided in the SAP.

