5.3.3.4 WHO OSCI

The WHO OSCI has values ranging from 0 to 8 as shown in [Table 6](#).

Table 6 WHO Ordinal Scale for clinical Improvement

Participant State	Descriptor	Score
Uninfected	No clinical or virological evidence of infection	0
Ambulatory	No limitation of activities	1
	Limitation of activities	2

Participant State	Descriptor	Score
Hospitalized – Mild disease	Hospitalized, no oxygen therapy	3
	Oxygen by mask or nasal prongs	4
Hospitalized – Severe Disease	Non-invasive ventilation or high flow oxygen	5
	Intubation and mechanical ventilation	6
	Ventilation + additional organ support	7
Dead	Death	8

The WHO OSCI will be recorded daily in the eCRF while participants remain in hospital. Once discharged, the WHO OSCI will be derived from questions 1 and 2 of the daily COVID-19 diary using the rules defined in [Table 7](#).

Table 7 Derivation of WHO OSCI using the Outpatient Daily Covid-19 diary

Question 1: Overall, how severe were your COVID-19 symptoms today?	Question 2: How much did your COVID-19 symptoms interfere with your usual activities today?	WHO OSCI Score
No COVID-19 symptoms today	Any response	0
Mild, moderate, severe or very severe	Not at all	1
Mild, moderate, severe or very severe	Somewhat or Very much	2

For participants who report question 1 as “No COVID-19 symptoms today” and a return to their usual activities (Q3) for 2 days in a row do not need to complete the COVID-19 diary on subsequent days. If this condition is met, the missing WHO OSCI score will be imputed as 0 for any remaining study days up to and including Day 42.

Note that participants who are discharged on home oxygen will still be considered as having WHO OSCI score =2 as the participant state is considered before the descriptor in [Table 6](#).

For participants who die, the WHO OSCI score will be imputed to 8 for all remaining study days after death.

WHO OSCI scores that are missing for reasons other than death or full recovery of symptoms will not be imputed.

For the secondary endpoint looking at whether participants remained at or below their baseline WHO OSCI score at Days 4, 7, 10, 14, 21 and 42, participants who show an increased score and then return to their baseline score (or lower) will not be considered as having met the criterion for this endpoint. Only participants who have not reported a score above their baseline score on any day prior to the endpoint day will be considered as having met the endpoint for that day.

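### Remaining at or below baseline OSCI: participants already counted as failures leave the denominator on later days if they withdraw for another experimental treatment

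*SAP*

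**What the plan says.** **The endpoint rule.** SAP 5.3.3.4 states that "participants who show an increased score and then return to their baseline score (or lower) will not be considered as having met the criterion". Success on a given day is limited as follows: "Only participants who have not reported a score above their baseline score on any day prior to the endpoint day". Failure therefore cannot be reversed. Once a rise is on record, the participant's status on every later day is known without a further score.

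**The exit rule.** SAP Table 11 (section 9.3.3.1) governs all the OSCI estimands, and this endpoint is named among them. Its last row concerns "Withdrawal from the study due to initiating other experimental treatment not considered standard of care before the study day of interest", and the strategy is "Participants will be excluded from the analysis at that study day". The row is labelled while-on-treatment. Death is handled separately, by carrying a score of 8 forward.

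**Other missing scores.** SAP 5.3.3.4 adds: "WHO OSCI scores that are missing for reasons other than death or full recovery of symptoms will not be imputed". Below Table 11 the SAP says: "Data missing for reasons other than an intercurrent event as detailed above will not be imputed". SAP section 8 bases percentages for categorical measures on the non-missing sample size.

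**The protocol.** For the start of another experimental treatment, Protocol Table 7 (section 9.3.2) says: "Values prior to starting experimental treatment will be used". Protocol 4.1 and 7.1 allow a participant admitted to ICU to join another interventional trial. Section 7.1 then says: "The participant is deemed to have completed this study at the point of signing the informed consent of this other study". SAP section 14 marks changes to the protocol as not applicable.

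**The concern.** Two SAP rules meet in the same participant and give opposite answers. Under 5.3.3.4, someone who worsened on Day 3 and left for another trial on Day 8 is a failure at Day 14. Under Table 11 that person is not in the Day 14 analysis. An excluded failure takes one from the denominator and nothing from the numerator, so the reported proportion can only rise.

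The exit is also linked to deterioration, because the protocol opens it at ICU admission.

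Prevention of progression is what the pilot sets out to investigate, and its results are meant to inform the size of later studies. The table for this endpoint (14.2.4.3) is also flagged for the DMC's efficacy review at 60 participants, where the decision to add 40 more has no predefined rule.

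**Working it through.** **Plan's own figure.** None is stated for this endpoint. The only precision table (SAP Table 8) concerns the trough S/F ratio. It reproduces (N = 60, SD 100: t(0.975, 58) × 100 × √(2/30) = 51.68, stated as 51.7) but does not bear on this question.

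**Inputs**
- 60 participants randomized 1:1, so 30 per arm (Protocol 9.1).
- Reported quantity: a proportion per arm with an exact 95% interval (SAP 9.3.3.2). The protocol also plans a difference in proportions (9.4.1.2).
- Failures per arm (w), and failures who leave after worsening and before the study day (k): the documents give neither, so both are assumed and varied.

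**One arm.** With all known failures kept, p = (30 − w)/30. With exclusion, p′ = (30 − w)/(30 − k). The inflation is p′ − p = p × k/(30 − k), which is positive whenever k > 0 and p > 0.

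| Failures w | Kept | k = 1 | k = 3 | k = 5 |
|---|---|---|---|---|
| 6 | 80.0% | 82.8% | 88.9% | 96.0% |
| 9 | 70.0% | 72.4% | 77.8% | 84.0% |
| 12 | 60.0% | 62.1% | 66.7% | 72.0% |

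For w = 9 and k = 3: 21/30 = 70.0% (exact 95% interval 50.6 to 85.3) becomes 21/27 = 77.8% (57.7 to 91.4). Over these assumptions the inflation is 2.1 to 2.8 points for one exit, 6.7 to 8.9 for three and 12.0 to 16.0 for five.

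**Difference, EDP1815 minus placebo** (30 per arm, assumed counts)

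| Failures, EDP1815 / placebo | Leave after worsening, EDP1815 / placebo | All failures kept | With exclusion |
|---|---|---|---|
| 9 / 9 | 0 / 3 | 0.0 | 21/30 − 21/27 = −7.8 |
| 9 / 9 | 3 / 0 | 0.0 | 21/27 − 21/30 = +7.8 |
| 9 / 9 | 2 / 2 | 0.0 | 21/28 − 21/28 = 0.0 |
| 6 / 9 | 1 / 3 | +10.0 | 24/29 − 21/27 = +5.0 |
| 3 / 6 | 1 / 2 | +10.0 | 27/29 − 24/28 = +7.4 |
| 3 / 6 | 2 / 2 | +10.0 | 27/28 − 24/28 = +10.7 |
| 3 / 6 | 3 / 0 | +10.0 | 27/27 − 24/30 = +20.0 |

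The difference can shrink, grow, change from zero in either direction, or stay put. It depends mainly on which arm loses more known failures.

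**Check on the remedy.** Keeping every known failure while dropping those who leave unworsened errs the other way. Take 30 participants, 6 failures and 6 leaving unworsened (assumed). The simple proportion is 18/24 = 75.0%, against 24/30 = 80.0% if none of those six would have worsened. Counting the six all as met gives 24/30 = 80.0%; all as not met gives 18/30 = 60.0%. Kaplan-Meier gives 75.0% if all six leave before the first failure, 80.0% if all leave after the last, and a value between these otherwise.

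**The case against.** Several points on the other side stand.

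- **Scope.** A reader might infer that everyone who withdraws is excluded. The explicit row covers one exit only. For other withdrawals, the SAP bars imputing a score, but failure can be derived from earlier scores with nothing imputed. Exclusion there is a plausible reading of the no-imputation rules and the non-missing denominator, not a stated rule.
- **Timing.** Known failures do not vanish altogether. Exclusion applies only to study days after the exit, and deaths on study stay in as 8. After ICU admission the default is to remain in the study to Day 42 where practical.
- **ICU is not the same as a rise.** A reader might infer that every ICU exit is a known failure. The OSCI has no ICU level, and SAP 7.2 allows a baseline score of 5, so a participant can enter ICU without rising. The documents give no frequency.
- **Direction.** A reader might infer that the difference is pulled toward zero. That holds if, for example, the same fraction of failures leaves each arm and placebo has more failures; nothing in the documents fixes those fractions. The 3 / 6 rows above show attenuation, almost no change and doubling.
- **Protocol conflict.** Protocol Table 7 is generic, and the protocol leaves the details of individual estimands to the SAP. For a score on a given day there is no pre-exit value to use. For this endpoint there is: the earlier rise itself.
- **Weight.** The analysis is descriptive, in a pilot without a power calculation. Maximum OSCI and ventilation-free survival keep the earlier worsening. At 80% v 90% with 30 per arm, the Wald 95% half-width is 1.96 × √(0.8 × 0.2/30 + 0.9 × 0.1/30), about 18 points. The 1 / 2 exit case shifts the difference by only 2.6 points (10.0 to 7.4).

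These points limit the concern. They do not remove it: the Table 11 row still excludes participants whose outcome is settled by 5.3.3.4.

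**Conclusion.** The concern holds in a limited form. For withdrawal to another experimental treatment, the SAP as written drops known failures from every later study day of this endpoint, against its own definition of failure and without declaring a departure from Protocol Table 7. For other withdrawals the text permits the same result but does not state it.

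Inflation of the affected arm's proportion follows by arithmetic, provided some participants in that arm met the endpoint. Its size rests on assumed counts: 7.8 points with 9 failures in 30 and 3 leaving after worsening. If no one who has worsened leaves, there is no effect. No direction can be claimed for the treatment difference. The point concerns one descriptive secondary endpoint and leaves the primary analysis untouched, but it is worth correcting before unblinding because the remedy uses scores already collected.

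**What to change.** 1. In SAP 5.3.3.4 and Table 11, state for this endpoint that a participant with any recorded post-baseline score above baseline up to and including Day X (death counting as 8) is not met at Day X and on all later days, whatever the later exit.
2. Make the main estimate at each day 1 minus the Kaplan-Meier cumulative incidence of first rise above baseline, censoring participants who leave without having worsened. Death is itself a rise, so it is an event and not a competing risk.
3. As a sensitivity range, report the simple proportions with unworsened leavers counted all as met and all as not met.
4. Reconcile Table 11 with Protocol Table 7, or record the departure in section 14. At the same time settle whether Day 10 belongs to this endpoint: SAP 5.3.3.4 and 9.3.3.2 include it, 9.3.3.1 does not.

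**Cost.** SAP wording and programming, with no new data. The main estimate assumes that censoring of unworsened leavers is independent of their later course, which is why the range in step 3 is needed. The exact binomial interval is replaced by a Kaplan-Meier interval.
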